11.0 STATISTICAL CONSIDERATIONS

11.1 Study Design/Endpoints

This multicenter, Phase I/II open label study will determine the safety and tolerability of participants with stage II/IV HIV-associated Hodgkin Lymphoma and evaluate the treatment effect of AVD in addition to brentuximab vedotin (SGN-35). The primary objective of the Phase I portion of the study is to identify the maximal tolerated doses of brentuximab vedotin when combined with the AVD chemotherapy regimen in HIV participants with advanced stage Hodgkin lymphoma. The primary objective of the Phase II portion of the study is to establish an estimate of the two-year progression-free survival for participants using brentuximab vedotin plus AVD regimen with HIV-associated advanced stage Hodgkin lymphoma.

Secondary objectives include:

- 1. To evaluate toxicity of AVD and brentuximab vedotin with HAART.
- 2. To estimate the partial response (PR) rate, complete response (CR) rate, overall survival (OS), event free survival at 2 and 5 years.
- 3. To evaluate effect of AVD and brentuximab vedotin on CD4 and CD8 counts after cycle 1, 4, at the end of therapy, and every 3 months after treatment completion for one year.
- 4. To investigate the prognostic value of FDG-PET/CT scans at baseline, after cycle 2, and at treatment completion, with respect to 2-year progression free survival.
- 5. To evaluate HAART status at baseline and to correlate this with tumor response to therapy and OS and PFS.
- 6. To characterize the histologic subtypes in HIV-HL in the highly active antiretroviral therapy (HAART) era.
- 7. To assess the neurotoxicity of HAART in combination with AVD and brentuximab vedotin.
- 8. To evaluate effect of AVD and brentuximab vedotin on viral load after cycles 1, 4, at completion of therapy, and every 3 months after treatment completion for one year.
- 9. To perform pharmacokinetic and immunogenicity studies to determine drug levels during therapy (see Section 10.0 and Appendix IX).
- 10. To perform miRNA profile analysis on the HIV-HL tumor specimens and to correlate miRNA expression with OS, PFS, tumor response to therapy, histologic subtype of HIV-HL, and HIV disease characteristics (see Section 10.0 and Appendix VIII).
- 11. To perform tissue microarray analysis on HIV-HL tumor specimens and to correlate the markers studied with OS, PFS, and tumor response to therapy (see Section 10.0 and Appendix VIII).
- 12. To identify EBV associated tumor derived DNA in the plasma of study participants, and to correlate these levels during therapy with disease response and OS (see Section 10.0 and Appendix XI). This objective will only be performed in the Phase II portion of the study.
- 13. To identify cytokines in the plasma of participants during therapy, that can be used as tumor and prognostic markers. (see Section 10.0 and Appendix X). This objective will be done only in the Phase II portion of the study.

14. To assess latent and expressed HIV reservoirs before, during, and post chemotherapy. To understand how cytotoxic chemotherapeutic agents effect HIV expression (see Section 10.0 and Appendix XII).

The Phase I portion of the clinical trial is a de-escalation design evaluating 3 doses of brentuximab vedotin (1.2 mg/kg, 0.9 mg/kg, and 0.6 mg/kg) given every 2 weeks with AVD in a 28-day cycle. Three to six participants will be enrolled at dose level 0. If > 1 DLT are encountered, an additional three to six participants will be enrolled at the next lowest dose level. If no more than 1/6th of the participants at the 0 dose level encounter a DLT, this dose (1.2 mg/kg) will be used in the phase II portion. If dose de-escalation is required, we will follow the algorithm presented in Table 4-A in Section 4.1.1.

The primary objective of the Phase I portion of the study is to identify the maximal tolerated doses of brentuximab vedotin when combined with the AVD chemotherapy regimen in HIV participants with advanced stage Hodgkin lymphoma. No formal statistical hypothesis testing is planned for the primary analysis on the Phase I safety parameters; results will be presented descriptively. Continuous data will be summarized for each cohort using descriptive statistics (N, mean, median, standard deviation, minimum, maximum, geometric mean, and percentage coefficient of variation [CV]). Categorical data will be summarized for each cohort using frequency tables (frequencies and percents).

The primary endpoint of the phase II portion will estimate the two-year progression-free survival for AVD-brentuximab vedotin which will be done using a one sample nonparametric survival analysis.

11.2 Sample Size/Accrual Rate

No formal statistical hypothesis testing is planned for the primary analysis of the Phase I portion of the study. In the Phase II portion of the study, 51 participants will be enrolled to estimate the 2-year progression free survival. Sample size calculation is based on providing an estimate of the PFS with a 95% confidence interval $\pm 10\%$ under the hypothesis that 2-year PFS is 85%.

If there are no DLTs in the Phase 1 portion of the study, and if 100% of the Phase 1 participants are treated identically to those in the Phase 2, data from the Phase 1 and 2 portions can be combined to complete the phase 2 portion of the study.

The primary endpoint of the phase II portion will be to estimate the two-year progressionfree survival for AVD-brentuximab vedotin which will be done using Kaplan-Meier estimates and corresponding 95% confidence intervals based on standard errors using Greenwood's formula.

11.3 Stratification Factors

No stratification is planned for this study.

11.4 Analysis of Secondary Endpoints

Descriptive summaries and exploratory analyses for secondary objectives will be conducted. Significance for comparisons will be at the p<0.05 level.

Secondary objectives include:

1. To evaluate toxicity of AVD and brentuximab vedotin with HAART.

- 2. To estimate the partial response rate, complete response rate, overall survival (OS), event free survival at 2 and 5 years. To evaluate effect of AVD and brentuximab vedotin on CD4 and CD8 counts after 2 cycles, 6 cycles, and every 3 months after treatment completion for one year.
- 3. To evaluate effect of AVD and brentuximab vedotin on viral load after 2 cycles, 6 cycles, and every 3 months after treatment completion for one year
- 4. To investigate the prognostic value of FDG-PET scans at baseline and after 2 cycles in participant with HIV and HL with respect to 2 year progression free survival.
- 5. To evaluate HAART status at baseline for difference in outcome.
- 6. The characterization of histologic subtypes in HIV-HL in the HAART era.
- 7. To assess additional neurotoxicity in combination with HAART and AVD and brentuximab vedotin.

The frequency of AEs and their severity will be tabulated to evaluate tolerance of AVD and brentuximab vedotin with HAART. Further, binomial probabilities and their 95% confidence intervals will be used to estimate the response rates (i.e., partial response rate, complete response rate, overall response rate) and event free survival at 2 and 5 years of AVD and brentuximab vedotin for a treatment of participants with stage III/IV HIV-associated Hodgkin Lymphoma.

Repeated measures analysis of variance (ANOVA) models will be used to evaluate the effect of AVD and brentuximab vedotin on CD4 counts, CD8 counts and viral load after 1, 4, and 6 cycles, and every 3 months after treatment completion for one year.

Log-rank analysis will be used to investigate the prognostic value of FDG-PET scans at baseline, after 2 cycles and post-therapy in participants with HIV and HL with respect to progression free survival.

After cycle 2 and post-therapy, progression-free survival will be estimated for participants whose FDG-PET findings were negative and those whose findings were positive using Kaplan-Meier estimates and corresponding 95% confidence intervals based on standard errors using Greenwood's formula. Positive predictive value after 2 cycles and post-therapy will be estimated as the proportion of PET-positive participants who progress or die before two years; negative predictive value after 2 cycles and post-therapy will be estimated as the proportion of PET-negative participants who are progression-free and alive at two years. Sensitivity of FDG-PET at cycle 2 and post-therapy will be estimated as the proportion of participants who progressed or died prior to year 2 whose FDG-PET was positive. Specificity of FDG-PET at cycle 2 and post-therapy will be estimated as the proportion of participants who are alive and progress-free at 2 years whose FDG-PET was positive. Exact two-sided 95% confidence intervals will be used for all estimates.

Log-rank analysis will be used to evaluate HAART status at baseline for difference in outcome in terms of overall survival and progression free survival. The frequency and proportion of different histologic subtypes will be calculated.

The frequency of neurotoxicity in participants taking AVD and brentuximab vedotin in combination with/without HAART will be tabulated. A binomial test of proportions will be used to test the difference in additional toxicity between those participants taking AVD

and brentuximab vedotin on HAART vs. those participants not on HAART.

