4.5 Study Duration

Participants will receive brentuximab vedotin in conjunction with standard, fixed, doses of doxorubicin 25 mg/m², vinblastine 6 mg/m², and dacarbazine 375 mg/m² on days 1 and 15 of a 28-day cycle for 6 cycles. Participants will be followed for a total of 5 years, every 3 months for the first 2 years and every 6 months for years 3 to 5 of follow up.

Participants who discontinue all protocol therapy after having a CR or PR are followed for up to 5 years after treatment for recurrence and survival. Participants who discontinue protocol therapy due to disease progression or other reasons (Section 4.6) are followed for survival only for up to 5 years after treatment or until death, whichever occurs first. Participants who cross over to non-protocol therapy (if PR or stable disease at physician discretion), or other reasons will be followed for survival for up to 5 years after treatment. Participants removed from study for unacceptable adverse event(s) will be followed until resolution or stabilization of the adverse event.

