4.6 Criteria for Permanent Removal from Treatment

After enrollment, participants will be permanently withdrawn from study treatment for any of the following reasons. In the event of withdrawal from treatment, the reason for study treatment removal and the date the participant was removed must be documented in the Off Protocol Treatment Form in AdvantageEDCSM. See Section 8.4 on evaluations to be performed at early discontinuation of therapy.

4.6.1 Participants who experience a delay of over 7 days in cycle 1 will be removed from protocol therapy. For subsequent cycles, if two sequential doses of AVD + BV or AVD alone are held due to unresolved toxicity, leading to a treatment delay of an
additional 2 weeks (i.e., 4 weeks between doses), the participant will be taken off protocol therapy. The participant will be followed for survival and may resume AVD treatment off study.

- 4.6.2 Severe toxicities as outlined in Section 5.0.
- 4.6.3 Progressive lymphoma at any time while on study.
- 4.6.4 Voluntary withdrawal.
- 4.6.5 The investigator has the right to remove participants from study for clinical reasons which he or she believes to be life threatening or resulting in significant morbidity to the participant.
- 4.6.6 Any participant who develops HBV reactivation or acute Hepatitis B as defined by the reappearance of a previously suppressed hepatitis B surface antigen, a positive IgM hepatitis B core antibody, and a positive viral load. Any participant with Hepatitis B or C who has worsening liver function as defined by Section 5.2.5 will also be removed from study.
- 4.6.7 Participants who become pregnant or breast-feed.
- 4.6.8 Participants with progressive disease at the end of cycle 2 will be removed from study treatment, while participants with stable disease may be removed from the study treatment at the discretion of the local responsible investigator. Progressive or stable disease defined at cycle 2 will be based by CT criteria only, as FDG-PET has yet to be validated in HIV-associated HL.
- 4.6.9 If found by central pathology review to not have the diagnosis of HIV-HL.

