8.2 Evaluations During Treatment

Evaluations are to occur in both Phase 1 and 2 and all study arms unless otherwise specified.

- 8.2.1 Update medical history prior to each cycle of chemotherapy. History to include concomitant medication changes and any signs and symptoms. Reportable adverse events must be recorded in AdvantageEDC. To be performed within 48 hours prior to or on first day of each cycle.
- 8.2.2 Physical examination prior to each cycle of chemotherapy. Examination to include performance status (Appendix III). All participants will be evaluated for clinical response by physical examination prior to receiving treatment on each cycle. The exam should occur within 2 days prior to the start of each cycle but may occur on Day 1 of cycle. Disease measurable by physical examination will be recorded in two dimensions if possible. To be performed within 48 hours prior to or on first day of each cycle.
- 8.2.3 FDG-PET/CT. Combined FDG-PET/CT or FDG-PET + CT scans with and without IV contrast are required for this study. If a participant has an allergy to IV contrast, a CT scan without contrast will be permitted.

Restaging evaluation by a full body FDG-PET/CT within Day 22-28 of Cycle 2 (i.e., 7-13 days after the Cycle 2 Day 15 doses of AVD-BV). If the CT portion of the PET/CT is a non-contrast CT, an additional CT scan with and without contrast must be obtained. Tumor measurements and SUVs must be documented. A neck CT must be included if palpable neck nodes were present at baseline and a diagnostic CT is being performed.

As the false positive rate of FDG-PET scans may be higher in the HIV population, a biopsy of an unexpected FDG-PET avid lesion is recommended but remains at the discretion of the investigator.

- 8.2.4 Neuropathy evaluation by completing the FACT/GOG-neurotoxicity questionnaire at the beginning of each cycle. To be performed once within 48 hours prior to or on first day of each cycle (Appendix IV).
- 8.2.5 CBC with differential within 48 hours of day 1 and 15 of each cycle. Results must

be known prior to treatment.

- 8.2.6 Serum chemistries within 48 hours of day 1 and 15 of each cycle: electrolytes (Na, K, Cl, bicarbonate, Ca, Mg, and phosphorus), glucose, blood urea nitrogen (BUN), creatinine, total bilirubin, alkaline phosphatase (ALP), LDH, total protein, albumin, AST and ALT. Results do not need to be known prior to treatment unless clinically indicated.

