The studies listed below will be performed post-therapy within 6-8 weeks of the last treatment dose (6-8 weeks after Cycle 6 Day 15; all follow up time points for post-treatment evaluations should be calculated in reference to this treatment discontinuation visit). Studies will then be repeated every 3 months (+/- 7 days) thereafter for 2 years; every 6 months (+/- 7 days) for the third through the fifth years unless otherwise specified. All study participants should be followed for up to 5 years after treatment discontinuation or until death if occurring before 5 years of treatment discontinuation. Participants who discontinue all protocol therapy after a CR or PR are followed for up to 5 years after treatment for recurrence and survival. Participants who discontinue protocol therapy due

to disease progression or other reasons are followed for survival for up to 5 years after treatment discontinuation. No additional studies except follow up for survival are required after disease progression. In those instances in which a third party payer denies payment for some or all of these laboratory analyses, absence of these test results will not be considered a protocol violation.

- 8.3.1 Medical history.
- 8.3.2 Physical examination, including performance status (see Appendix III, Performance Status Scale), vital signs (weight, height, body surface area), neurological examination, and if possible, two dimensional measurement of all palpable, peripheral lymph nodes and measurement of other sites of disease present on physical exam.
- 8.3.3 At the conclusion of chemotherapy, a full body FDG-PET/CT scan will be done between 6-8 weeks post the final treatment dose, Cycle 6 Day 15. This will be the final FDG-PET/CT needed for the study. A combined FDG-PET/CT or FDG-PET + CT scans with and without IV contrast are required for the post-treatment scan. If a participant has an allergy to IV contrast, a CT scan without contrast will be permitted. As the false positive rate of FDG-PET scans may be higher in the HIV population, a biopsy of an unexpected FDG-PET avid lesion is recommended but remains at the discretion of the investigator.
- 8.3.4 CT scan with oral/IV contrast every 6 months for 5 years. To begin 6 months from the post treatment FDG-PET/CT scan, obtained 6-8 weeks post the final chemotherapy dose (See Section 8.3.3).

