8.4 Early Discontinuation of Therapy

- 8.4.1 Participants discontinuing therapy early (i.e., PD or stable disease, administrative reasons, participant non-compliance, etc.) will have a medical history update and complete physical examination. The examination will include performance status and blood drawn for the following studies within 1 month after treatment discontinuation, unless otherwise noted. See Section 4.7 for a list of reasons for study termination. Participants will be followed for survival only for 5 years after the last date of treatment:
 - 8.4.1.1 CBC with differential.
 - 8.4.1.2 Serum chemistries: electrolytes (Na, K, Cl, bicarbonate, Ca, Mg, and phosphorus), glucose, blood urea nitrogen (BUN), creatinine, total bilirubin, alkaline phosphatase (ALP), LDH, total protein, albumin, AST and ALT.
 - 8.4.1.3 CD4 and CD8 cell count (do not repeat if done within 1 month from removal from treatment).
 - 8.4.1.4 HIV-1 RNA viral load to be assessed by any FDA-approved viral load assay (evaluated at the local laboratory, do not repeat if done within 1 month from removal from treatment).
 - 8.4.1.5 Pharmacokinetic/Immunogenicity studies in select Phase II participants only. See Section 10.1 and Appendix IX for time points and sample processing.
 - 8.4.1.6 Blood samples will be taken for analysis of latent and HIV reservoirs. See Section 10.0 and Appendix XII for time points needed, sample processing, and shipping instructions (do not repeat if done within 1 month from removal from treatment).
 - 8.4.1.7 Plasma samples to be taken for EBV tumor DNA studies. See Appendix XI for sample processing and shipping instructions. This will only be performed on the Phase II portion of the study.
 - 8.4.1.8 Plasma samples to be taken for and cytokine studies. See Appendix XI for sample processing and shipping instructions. This will only be performed on the Phase II portion of the study.

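### Event-free survival at 2 and 5 years is estimated as a binomial proportion, with no rule for unknown status, while PFS uses Kaplan-Meier

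*Combined protocol and SAP*

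**What the plan says.** In AMC Section 11.4, "binomial probabilities and their 95% confidence intervals will be used to estimate the response rates", and the same sentence goes on to cover EFS: it is to "estimate the response rates (i.e., partial response rate, complete response rate, overall response rate) and event free survival at 2 and 5 years". LYSARC 16.4 has the same sentence. For the primary endpoint, AMC 11.2 and LYSARC 16.2 specify "Kaplan-Meier estimates and corresponding 95% confidence intervals based on standard errors using Greenwood's formula", and the PFS analysis by PET result uses the same method. Neither protocol gives a time-to-event estimate of EFS, a definition of EFS, or a rule for participants whose EFS status is unknown at 2 or 5 years.

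The follow-up rules determine whose status can be unknown:

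- **AMC 8.3:** "Participants who discontinue all protocol therapy after a CR or PR are followed for up to 5 years after treatment for recurrence and survival".
- **AMC 4.5:** those who stop for progression or for other reasons "are followed for survival only for up to 5 years after treatment or until death, whichever occurs first".
- **AMC 4.6.1** (removal for a toxicity delay): "The participant will be followed for survival and may resume AVD treatment off study".
- **AMC 8.4** (early discontinuation in general): "Participants will be followed for survival only for 5 years after the last date of treatment".

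LYSARC 9.5 and 9.6 carry the same text as AMC 8.3 and 8.4. Text on withdrawal of consent and loss to follow-up appears only in LYSARC 13.2 and 13.3, which covers 20 of the 51 planned participants.

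**The concern.** EFS is a time-to-event endpoint, but the plan handles it like a response rate. A binomial proportion at 2 or 5 years cannot use partial follow-up. A participant known to be event-free at 4 years and then lost has no place in a 5-year proportion unless someone decides where to put them. Two analysts could both follow the plan and report different EFS values from the same data. EFS at 2 and 5 years is a named secondary objective in both protocols, so its estimator should give one answer.

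**Working it through.** **The plan's own figure.** For a 95% interval of ±10 points at a 2-year PFS of 85% (AMC 11.2): n = 1.96² × 0.85 × 0.15 / 0.10² = 48.98, so 49. At the planned 51 the half-width is 1.96 × √(0.85 × 0.15 / 51) = 9.8 points. The sample size is consistent with its stated basis and is not in dispute.

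**Who can have unknown status.** Participants who stop after CR or PR stay under follow-up for recurrence (AMC 4.5 and 8.3). Those who stop for progression already have an event under any usual EFS definition. That leaves participants lost or withdrawn, and those who stop with neither a response nor progression. Removal for a toxicity delay in cycle 1 is one such route. It comes before the first scheduled scan ("Restaging evaluation by a full body FDG-PET/CT within Day 22-28 of Cycle 2", AMC 8.2), so no imaging response exists, and follow-up is then for survival. AMC 8.4 read literally would put every early discontinuation on survival-only follow-up, which conflicts with 4.5 and 8.3. LYSARC 9.6 conflicts with 9.5 in the same way.

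**Complete status.** With 8 events among 51, the binomial estimate is 43/51 = 84.3%, SE √(0.843 × 0.157 / 51) = 5.1 points. Kaplan-Meier with Greenwood gives 84.3% and 5.1 points. Changing the estimator loses nothing.

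**Incomplete status, from the documents alone.** Each unknown puts event-free and failure 1/51 = 2.0 points apart; three unknowns give 3/51 = 5.9 points. This is a gap between conventions, not an expected error.

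**Illustration.** The assumptions are:

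- The 85% 2-year PFS hypothesis is borrowed as a ceiling for EFS.
- The hazard is constant, so 5-year EFS is 0.85^2.5 = 66.6%.
- A proportion L = 10% or 20% is lost by 5 years, independently of outcome.

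With time t in months, λ = −ln(0.85)/24 and μ = −ln(1−L)/60:

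- observed events: E = λ/(λ+μ) × (1 − exp(−(λ+μ)t))
- known event-free: A = exp(−(λ+μ)t)
- unknowns counted event-free: 1 − E; dropped: A/(A+E); counted as failures: A

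| Time (true EFS) | Loss by 5 years | Expected unknown of 51 | Event-free | Dropped | Failures |
|---|---|---|---|---|---|
| 2 years (85.0%) | 10% | 1.9 | 85.3% | 84.7% | 81.5% |
| 2 years (85.0%) | 20% | 4.0 | 85.6% | 84.4% | 77.7% |
| 5 years (66.6%) | 10% | 4.2 | 68.2% | 65.3% | 60.0% |
| 5 years (66.6%) | 20% | 8.4 | 69.8% | 63.9% | 53.3% |

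The 95% half-width at 5 years is 1.96 × √(0.666 × 0.334 / 51) = 12.9 points.

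**Second starting value.** AMC 2.3 cites a 5-year EFS of 71% for an ABVD study. With 71% as the true value and 20% lost by 5 years, simulation with n = 51 gives a binomial mean of 73.8% (event-free), 68.3% (dropped) or 56.6% (failures), against 70.9% by Kaplan-Meier.

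**If results are reported early.** At 2 participants per month (AMC 3.3.2), entries fall at months 0, 0.5, …, 25. At month 72, 25 of the 51 have 60 months of potential follow-up. In simulation with no losses, the 5-year half-width is about 18.3 points for the binomial on those 25 and 13.6 for Kaplan-Meier on all 51. By about month 85 everyone has reached 5 years and this difference is zero.

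**The case against.** The strongest reply is that the estimator is not the root of the ambiguity. A binomial estimate with a stated rule for unknowns is reproducible. Kaplan-Meier without defined events, origin and censoring is not, and copying the PFS method supplies no censoring rule because none is written for PFS either. Kaplan-Meier also assumes non-informative censoring, which is doubtful for removals for toxicity. If EFS were meant to count removal from treatment as an event, those participants would have known status. All of this stands. It is why the definition and censoring rule must accompany the change of estimator.

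The size is also modest. Under two of the three conventions the shift is well inside the interval width, and no text proposes counting unknowns as failures. The month-72 case deserves little weight: LYSARC 19.6 makes publication after complete data collection the default, although it allows partial results earlier, and LYSARC 19.9 places the report after the end of the study.

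The 51 is approximate too. The EFS objective covers both phases, and the 11.4 sentence refers to stage III/IV although AMC eligibility is stage II–IV. Finally, the plan labels its secondary analyses descriptive and exploratory.

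None of this supports the binomial over Kaplan-Meier for EFS. It is never better, and it discards information whenever follow-up is partial.

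**Conclusion.** The concern holds. Both protocols assign EFS at 2 and 5 years to an estimator that requires complete status, without saying what to do when status is incomplete, although the plan already uses a suitable method for PFS. The effect is nil with complete status. Under the assumed losses, dropping unknowns or counting them event-free costs 0.3 to 0.6 points at 2 years and 1.3 to 3.2 at 5 years. Counting them as failures costs 6.7 or 13.3 points at 5 years. These figures rest on an assumed loss rate, a constant hazard, losses independent of outcome, and the PFS hypothesis standing in for EFS. No decision depends on EFS, so this is a recommended correction and does not threaten the trial's main result.

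**What to change.** In AMC 11.4 and LYSARC 16.4:

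1. Keep binomial estimates with 95% intervals for PR, CR and overall response only.
2. Estimate EFS at 2 and 5 years by Kaplan-Meier with Greenwood 95% intervals. Do the same for OS at 2 and 5 years, for which no estimator is named; the plan gives only a log-rank comparison by HAART status.
3. Define the EFS events, time origin and censoring date, including how a participant on survival-only follow-up is handled.
4. Report the number censored before 2 and before 5 years, since Kaplan-Meier still relies on non-informative censoring.

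Separately, reconcile AMC 8.4 with 4.5 and 8.3, and LYSARC 9.6 with 9.5, on who is followed for recurrence.

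The estimator change is wording in two statistical sections. It uses the same data, method and software as the primary PFS analysis and leaves the sample size at 51.
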